3 OBJECTIVES AND ENDPOINTS

3 OBJECTIVES AND ENDPOINTS					
OBJECTIVES	ESTIMANDS	ENDPOINTS			
Primary objectives					
To describe the safety and tolerability of BNT165b1 vaccination in healthy adults.	 For each DL cohort: Frequency of solicited local reactions at the injection site recorded up to 7 d after each dose. Frequency of solicited systemic reactions recorded up to 7 d after each dose. Proportion of subjects with at least one AE occurring up to 28 d after each dose. Proportion of subjects with at least one MAAE occurring up to 28 d after each dose. Proportion of subjects in each cohort with at least one SAE occurring up to 24 weeks after Dose 3. 	 Solicited local reactions (pain, erythema/redness, induration/swelling) Solicited systemic reactions (vomiting, diarrhea, headache, fatigue, myalgia, arthralgia, chills, and fever) AEs SAEs MAAEs 			
Exploratory objectives					
To describe the humoral immune responses induced by BNT165b1 vaccination at different DLs in healthy adults.	Not applicable	Levels of antigen-specific serum and/or plasma antibodies (total IgG) measured using ELISA and/or similar assays CCI			
CCI					

Page 26 of 82 Version: 4.0 Date: 13 FEB 2023

Abbreviations: AE = adverse event; CCI d(s) = day; DL(s) = dose level(s); ELISA = enzyme-linked immunosorbent assay; IgG = immunoglobulin G; MAAE = medically attended adverse event; SAE = serious adverse event.

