6.3.2.2 Blinding of trial site personnel

The trial personnel dispensing and administering the vaccine will be unblinded, but all other trial personnel, including the principal investigator, and the subject, will be blinded. The principal investigator will assign the responsibility of unblinded dispenser and unblinded administrator to persons who will not participate in the evaluation of any trial subject. More than one unblinded dispenser/administrator may be assigned. A member of

Clinical Trial Protocol Trial number: BNT165-01 Page 36 of 82 Version: 4.0 Date: 13 FEB 2023

the trial site personnel or clinic pharmacy should fulfill this role. Contact between the unblinded dispenser/administrator and trial subjects should be kept to a minimum.

The investigator and any site personnel other than the unblinded dispenser/administrator must not be allowed to know the IMP assigned to any trial subject and must not be allowed to see the drug product containers.

Because BNT165b1 and placebo differ in their physical appearance, the trial treatment will be provided in a manner that maintains the blinding, e.g., syringes will be masked or colored. For details, see the Pharmacy Manual.

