7.1.1 Cohort trial treatment pausing rules

Grading scales for the intensity of AEs and SAE will be based on guidance from the US Food and Drug Administration "Toxicity Grading Scale for Healthy Adult and Adolescent Volunteers Enrolled in Preventive Vaccine Clinical Trials".

If any of the below is met in a given cohort and after any dose, no additional trial subjects will be assigned to the cohort and administration of trial treatment, including administration of Dose 2 and/or Dose 3 for affected cohorts and any higher DL(s), will be paused until the IRC reviews the event(s):

- Any SAE developed by subject administered with trial treatment (at any DL), for which there is no alternative, plausible, attributable cause and which is assessed by the investigator, or the sponsor as possibly related.
- Any severe (Grade 3) hypersensitivity or any anaphylactic AE that occurs within 7 d
 of vaccination without a clear alternative cause.

NOTE: Grade 3 hypersensitivity is defined as symptomatic bronchospasm with or without urticaria, parenteral intervention, allergy related edema/angioedema, or hypotension. Grade 4 hyposensitivity encompasses all life-threatening events and for which urgent intervention is indicated.

Clinical Trial Protocol Trial number: BNT165-01 Page 40 of 82 Version: 4.0

Date: 13 FEB 2023

- Any Grade 4 AE after administration of trial treatment (at any DL) that is assessed as possibly related by the investigator, or for which there is no alternative, plausible, attributable cause.
- Any case of immune-related AE, including but not limited to myocarditis, pericarditis or myopericarditis, that is assessed as possibly related by the investigator, or for which there is no alternative, plausible, attributable cause.
- Any case of fever >40.0°C (measured orally) persisting for over 6 h despite the use of antipyretics after administration of trial treatment (at any DL) that is assessed as possibly related by the investigator and/or sponsor, or for which there is no alternative, plausible, attributable cause.
- If two trial subjects develop the same or similar Grade 3 or higher AE at least possibly related to trial treatment (solicited injection site reactions, solicited systemic reactions, unsolicited AEs, and laboratory abnormalities considered at least possibly related to trial treatment).

NOTE:

- Reactogenicity e-diary data confirmed by the investigator as being entered by the subject in error will not contribute toward a pausing rule.

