It is sufficient to document the causality in the source data and CRF as:

- Related (= there is a reasonable possibility of a causal relationship) or
- Not related (= there is no reasonable possibility of a causal relationship)

The relationship or association of an AE or SAE to a trial treatment/trial procedure will be assessed by the investigator after having evaluated all accessible data and, if necessary, he/she will re-evaluate the case as new information becomes available.

Events caused by the procedure of trial treatment administration should be differentiated from events caused by the trial treatment itself. Only events suspected to be caused by the IMPs itself should be documented as suspected adverse reactions but not events caused by the procedure of trial treatment administration.

In this trial, it cannot be excluded that during the course of the trial some procedures give rise to AEs which are related to the trial procedure and not to the trial treatment. Procedure-related AEs can occur on the site of injection of the trial treatment (e.g., redness, swelling, hematoma or itching) or during or after trial-specific procedure (e.g., discomfort after blood drawing). These events must be reported in the CRF on Adverse Event pages as "related to trial procedure" with the causing procedure specified.

Notes applicable for relationship to trial procedures including trial treatments

There may be situations in which an SAE has occurred, and the investigator has minimal information to include in the initial report to the sponsor. However, it is very important that the investigator always makes an assessment of causality for every event before the initial transmission of the SAE data to the sponsor.

The investigator may change their opinion of causality in light of follow-up information and send a SAE follow-up report with the updated causality assessment.

The causality assessment is one of the criteria used when determining regulatory reporting requirements.

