8.5.4.2 Adverse event summaries by SOC, PT and grade

The number and percentage of subjects reporting unsolicited AEs occurring up to 28 days post each dose and regardless of the number of doses will be summarized by PT nested within SOC and by grade. AEs with a missing grade will be presented in the summary table with a grade category of "Missing".

Similar analyses will be provided for:

- SAEs (from Day1 through Visit 14)
- SAEs related to IMP (from Day1 through Visit 14)
- AEs related to IMP (from Day 1 through 28 days post each dose and regardless of the number of doses)
- Solicited AEs that continue longer than 7 d post-dose or are a SAE (from Day 1 through 28 days post each dose and regardless of the number of doses)
- MAAEs (from Day 1 through 28 days after each dose)
- Non-serious AEs (from Day 1 through 28 days post each dose and regardless of the number of doses)
- AEs leading to study withdrawal (any such AEs reported during the study)
- AEs leading to IMP discontinuation (any such AEs reported during the study)

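### Protocol 10.4.3 lists injection-site redness and swelling as procedure-related examples with no rule for telling them from vaccine reactions, so attribution to the IMP can differ between sites

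*Protocol*

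**What the plan says.** Under the assessment of causality, protocol 10.4.3 asks for a split by cause: "Events caused by the procedure of trial treatment administration should be differentiated from events caused by the trial treatment itself". It goes on: "Only events suspected to be caused by the IMPs itself should be documented as suspected adverse reactions but not events caused by the procedure" of administration. It then gives examples, "Procedure-related AEs can occur on the site of injection of the trial treatment (e.g., redness, swelling, hematoma or itching", and instructs: "These events must be reported in the CRF on Adverse Event pages as" related to trial procedure, with the procedure named. The same section calls an event related when a causal link is a reasonable possibility.

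Other parts of the plan treat the same signs as vaccine reactogenicity or depend on the relatedness call:

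- Protocol 3 has as a primary endpoint "Solicited local reactions (pain, erythema/redness, induration/swelling".
- Protocol 7.1.1 applies its two-subject pausing rule to "solicited injection site reactions, solicited systemic reactions, unsolicited AEs, and laboratory abnormalities considered at least possibly related to trial treatment".
- Protocol 6.3.2.2 says that, apart from those who dispense and administer the vaccine, "all other trial personnel, including the principal investigator, and the subject, will be blinded".
- SAP 8.5.4.1 has rows for related AEs and related AEs of Grade 3 or higher. SAP 8.5.4.2 tabulates "AEs related to IMP (from Day 1 through 28 days post each dose and regardless of the number of doses". Neither section has a procedure-related category.

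**The concern.** Two of the four signs that 10.4.3 gives as procedure examples, redness and swelling, are also solicited reactions in the primary endpoint. The section offers no criterion, such as timing, size or duration, for deciding which cause applies, and it does not exempt solicited terms. The investigator cannot use the treatment arm to decide. The trial is multi-center (protocol 4.1), so two sites could see the same persistent swelling and record it differently, each in good faith.

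At stake is the count of events attributed to the vaccine in a first-in-human trial, and the safety triggers that need a possible relation to treatment. The placebo group exists to show what the injection alone produces. Asking investigators to remove that part event by event does the same job less reliably.

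**Working it through.** **1. The plan's own figure.** The only operating figure in the documents is in protocol 9.2 and SAP 6: the chance of at least one AE in 20 subjects. It reproduces: 1 − 0.90^20 = 0.878 (stated 88%) and 1 − 0.85^20 = 0.961 (stated 96%). This point does not depend on it.

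**2. Where causality coding has no effect.**
- SAP 8.5.2.1 counts solicited local reactions from e-diary entries and grades them by maximum severity, with no causality filter.
- The same section counts local reactions persisting beyond 7 days, for any grade and for Grade 3 or higher.
- SAP 8.5.4.1 and 8.5.4.2 tabulate solicited events that last past 7 days or are SAEs, whatever their cause. SAP 8.5.4.1 also has all-cause rows for AEs of Grade 3 or higher and for SAEs.

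**3. Where it does have an effect.**
- *Related-AE rows (SAP 8.5.4.1 and 8.5.4.2).* Protocol 8.2.7 and SAP 8.5.4 keep most solicited reactions off the AE page. The exposed events are local reactions that last past Day 7, are serious or are reported as unsolicited.
- *Delayed reactions.* Those found at the 14-day call are only listed (SAP 8.5.2). If one is also reported as an AE, the AE tables are the only place where it is tabulated.
- *Triggers.* These are the two-subject rule (protocol 7.1.1), the 24-hour notice of Grade 3 or higher events (7.1 and 8.3.2) and the individual Grade 4 criterion (7.1.3). All turn on a possible relation.
- *No recovery rule.* SAP 8.5.4 sets a missing relationship to related. An event entered as procedure-related is not missing, so that default does not reach it.

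**4. A gap between the passages.** Protocol 10.4.3 sends procedure-related site reactions to the AE page, while protocol 8.2.7 and SAP 8.5.4 keep shorter solicited reactions off it. No causality field for e-diary reactions is described, although 7.1.1 needs a causality judgment on them.

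**5. Size in the related-AE rows.** There are 16 vaccinees per dose level (protocol 9.2). If k of them have their only related AE recoded, the proportion falls by k/16: 6.25 points for k = 1, 12.5 for k = 2, 18.75 for k = 3. The documents do not give k.

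**6. Illustration for the two-subject rule.** Let p be the true rate of the same Grade 3 or higher local reaction and q the share coded as procedure-related. Both are assumptions. With r = p(1 − q), the chance that at least 2 of 16 vaccinees count is 1 − (1 − r)^16 − 16r(1 − r)^15.

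| p | q = 0 | q = 25% | q = 50% | q = 75% | q = 100% |
|---|---|---|---|---|---|
| 5% | 0.189 | 0.119 | 0.059 | 0.017 | 0 |
| 10% | 0.485 | 0.340 | 0.189 | 0.059 | 0 |
| 15% | 0.716 | 0.551 | 0.340 | 0.119 | 0 |
| 20% | 0.859 | 0.716 | 0.485 | 0.189 | 0 |

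For example, at p = 10% and q = 50%, r = 0.05 and the chance is 1 − 0.440 − 0.371 = 0.189, against 0.485 with no recoding.

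**The case against.** The strongest reply is that 10.4.3 is conditional. It says procedure-related events can occur at the injection site, and its coding instruction covers only events already judged to be of that kind. An investigator who cannot tell needle effect from vaccine effect should, on the section's own reasonable-possibility standard, record the event as related. The section also asks for the timing of the event to be weighed, and late onset argues against needle trauma. This stands. A reader might infer that sites are told to code all injection-site redness and swelling as procedure-related; the text does not say that.

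A reader might also infer that the vaccine's local reactions drop out of the primary results. They do not: the e-diary tables ignore causality, and persistent or serious reactions remain in all-causality rows. What can be lost is attribution, not the event.

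On pausing, 7.1.1 names solicited injection-site reactions and sets a low threshold. The investigator confirms Grade 3 or higher local reactions (protocol 8.2.6.1), and the Medical Monitor and Safety Physician assess whether a rule is met (4.1). The IRC includes unblinded sponsor personnel (6.3.2.5) and can meet without a rule being met (7.1). These safeguards make a missed event less likely. They do not close the gap, because the automatic trigger and the expedited notice still rest on the relatedness call.

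**Conclusion.** The conflict is real but narrow. Protocol 10.4.3 gives two primary solicited signs as procedure examples, supplies no criterion for separating them from vaccine reactions, and leaves the decision to blinded investigators at several sites. The effect is confined to attribution to the IMP in the related-AE rows, for local reactions that last past Day 7, are serious or are reported as unsolicited, and to the triggers that need a possible relation.

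The size is 6.25 percentage points of a dose-level related-AE proportion for each recoded vaccinee who has no other related AE. The number recoded is unknown, and the pausing table shows only how sensitive the rule is under assumed rates. The frequencies in protocol 4.2 for the related COVID-19 vaccine (injection-site pain above 80%, swelling above 10%) cannot size the problem. They describe reactions that usually resolved within a few days, and most such reactions never reach the related-AE rows.

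The verdict rests on two readings. Coding to procedure is taken as an alternative to coding to the IMP, as the instruction to separate the two causes implies. The related rows in SAP 8.5.4.1, which do not say related to what, are taken to mean related to the IMP, in line with SAP 8.5.4.2.

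**What to change.** - **Protocol 10.4.3, examples.** Remove redness, swelling and itching at the IMP injection site from the procedure-related examples. Keep hematoma, venipuncture and other trial procedures.
- **Protocol 10.4.3, rule.** State that an injection-site reaction is recorded as related to IMP when an IMP contribution is a reasonable possibility. The pooled placebo group (SAP 8.1) then shows the contribution of the injection itself.
- **SAP 8.5.4.** Keep the investigator's recorded causality in the main related-AE tables. Add a sensitivity row that also counts injection-site reactions coded to trial procedure with the IMP injection as the named cause.
- **Reconciliation.** Bring protocol 10.4.3 into line with protocol 7.1.1, 7.1.3 and 8.2.7 and SAP 8.5.4 on how these reactions are recorded and treated for pausing and discontinuation. Which rule applies is for the sponsor to settle; this review does not propose one.

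The cost is a short protocol edit, one extra row in the related-AE tables and the reconciliation. The downside is that a few needle-trauma events will count as related, in both vaccine and placebo recipients.

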10.4.4 Reporting of SAEs

All SAEs (defined in Section 10.4.2) which occur in a trial subject during the observation period, whether considered to be associated with trial medication or not, must be reported by the investigator to the sponsor within 24 h following first knowledge of the event.

All SAEs occurring after the end of the period of observation only have to be reported to the sponsor if the investigator suspects a relationship to trial medication or the trial procedure.

SAE reporting to the sponsor using paper report forms

The investigator must ensure the respective paper report form is completed and transmitted to the sponsor via one of the following reporting lines:

Clinical Trial Protocol Trial number: BNT165-01 Page 74 of 82 Version: 4.0 Date: 13 FEB 2023

Safety Report Fax No.:
 Safety Report E-Mail address:

As of 01 MAR 2023, the following reporting lines apply:

Safety Report Fax No.:
 Safety Report E-Mail address:

In parallel the respective SAE should be recorded in EDC as soon as possible.

Information for the final description and evaluation of a case report may not be available within the required time frames for reporting. Nevertheless, for regulatory purposes, initial reports should be submitted if the following minimal information is available:

- An identifiable trial subject (subject number)
- A suspected medicinal product
- An identifiable reporting source (investigator/trial site identification)
- An event or outcome that can be identified as serious

For SAEs, follow-up information should be sent to the sponsor (indicating that this is a "follow-up" report using the respective SAE Form or the Additional Information and Follow-Up Form) without delay as described above and accompanied by appropriate anonymous supporting documentation (e.g., discharge letters, medical reports or death certificates), until a final outcome and date are available. All confidential information (name, address, full date of birth) needs to be blackened before sending.

For SAEs in addition to a medical record, the investigator should complete an Additional Information and Follow-Up Form, which contains the event term and subject number.

A copy of the submitted SAE report must be retained on file by the investigator. If explicitly required according to national legislation, the investigator must submit copies of the SAEs to the IRB/IEC or authority and retain documentation of these submissions in the Site Trial File.

10.4.5 Assessment of laboratory abnormalities

Laboratory abnormalities will be graded according to the US FDA "Toxicity Grading Scale for Healthy Adult and Adolescent Volunteers Enrolled in Preventive Vaccine Clinical Trials".

Page 75 of 82 Version: 4.0 Date: 13 FEB 2023

10.5 Contraceptive guidance and collection of pregnancy information

The following definitions and guidance is based on the Clinical Trial Facilitation Group (CTFG) recommendations related to contraception and pregnancy testing in clinical trials issued in 2020 (CTFG 2020).

10.5.1 Definitions

Volunteer of childbearing potential

For the purpose of this document, a volunteer born female is considered of childbearing potential, i.e., fertile, following menarche and until becoming postmenopausal unless permanently sterile. Permanent sterilization methods include hysterectomy, bilateral salpingectomy and bilateral oophorectomy.

If fertility is unclear (e.g., amenorrhea in adolescents or athletes or during cancer treatment), additional evaluation should be considered.

Women in the following categories are not considered VOCBP:

- Premenarchal
- Premenopausal female with one of the following:
 - Documented hysterectomy
 - Documented bilateral salpingectomy
 - Documented bilateral oophorectomy

For trial subjects with permanent infertility due to a medical cause other than the above, (e.g., mullerian agenesis, androgen insensitivity), investigator discretion should be applied to determining trial entry.

Postmenopausal female

For the purpose of this document, a postmenopausal state is defined as no menses for 12 months without an alternative medical cause.

A high follicle stimulating hormone level in the postmenopausal range may be used to confirm a postmenopausal state in women not using hormonal contraception or hormonal replacement therapy (HRT). However, in the absence of 12 months of amenorrhea, confirmation with more than one follicle stimulating hormone measurement is required.

Females on HRT and whose menopausal status is in doubt will be required to use one of the non-estrogen hormonal highly effective contraception methods if they wish to continue their HRT during the trial. Otherwise, they must discontinue HRT to allow confirmation of postmenopausal status before trial enrollment.

Fertile men

For the purpose of this document, a man is considered fertile after puberty unless permanently sterile by bilateral vasectomy or orchidectomy.

Page 76 of 82 Version: 4.0 Date: 13 FEB 2023

10.5.2 Contraception guidance

The following guidance describe what is considered highly effective and acceptable methods of contraception.

The investigator or delegate should advise the trial subject how to achieve highly effective contraception.

The following birth control methods that can achieve a failure rate of less than 1% per year when used consistently and correctly may be considered as highly effective:

- Combined estrogen and progestogen-based hormonal contraception associated with inhibition of ovulation ¹, i.e., established use of (oral, intravaginal, or transdermal) hormonal methods of contraception.
- Progesterone-only based contraception associated with inhibition of ovulation ¹, i.e., established use of (oral, injected, or implanted) hormonal methods of contraception. ²
- Intrauterine device. ²
- Intrauterine hormone-releasing system.²
- Bilateral tubal occlusion.²
- Bilateral vasectomy (for a male trial subject or male partner of a female trial subject). ^{2, 3}
- Sexual abstinence ⁴
- 1 Hormonal contraception may be susceptible to interaction with the IMP, which may reduce the efficacy of the contraception method.
- 2 Contraception methods that in the context of this guidance are considered to have low user dependency.
- 3 A vasectomized partner is a highly effective birth control method provided that partner is the sole sexual partner of the VOCBP trial subject and that the vasectomized partner has received medical assessment of the surgical success.
- In the context of this guidance sexual abstinence is considered a highly effective method only if defined as refraining from heterosexual intercourse during the entire period of risk associated with the trial treatments. The reliability of sexual abstinence needs to be evaluated in relation to the duration of the clinical trial and the preferred and usual lifestyle of the trial subject.

